5.4 REMOTE CONSENT & ENROLLMENT

When studying resistance mechanisms arising in ALK positive lung cancer patients upon progression on ALK inhibitors, we are limited not only by the small amount of tumor tissue usually available for genomic testing but also by the tiny number of lung cancer patients harboring an ALK rearrangement, only a 4-7% of the total lung cancer population. To overcome this limitation, we plan to leverage a remote consent and participation approach to allow every metastatic ALK positive NSCLC patient across the nation to enroll in this study. The web-based consent form utilized will allow participants to be directed for help and ask questions during the consent process. Study coordinators will receive a notification and respond to the questions in a timely manner. By using a web-based remote consent process every ALK positive NSCLC patient living in the Continental US (including Alaska, Hawaii and US Territories), with disease progression while on a next generation ALK TKI will be considered a potential candidate.

Our group (DFCI and ALCMI) has previous experience with a remote consent approach both web and paper-based. In the Genomics of Young Lung Cancer study (GoYLC), DFCI co-led a web-based remote participation study for patients under the age of 40 diagnosed with lung cancer in the Investigating Hereditary Risk from T790M (INHERIT) study, DFCI led a paper-based remote consent process for patients and subjects harboring germline T790M mutation. Those two populations, patients younger than 40 years old at diagnosis and those harboring a germline *T790M*, are extremely uncommon conditions²⁰. However, by using a remote consent and participation approach, 136 patients over 36 months and 121 subjects over 60 months were included in the GOYL and INHERIT studies, respectively. ²⁰. If we consider that for example, germline T790M is present in around 1/1.000 lung cancers the accrual rate achieved in INHERIT study underlines the incredible power of remote participation studies to study uncommon populations in a timely manner. By using the same approach to study ALK TKI resistance in ALK-positive lung cancer, a more prevalent condition

Title: Study of Plasma Next Generation Sequencing for Remote Assessment, Characterization, Evaluation of Patients With ALK Drug Resistance (SPACEWALK)

found in 3-5% of lung cancers, we consider we will be easily able to accrue at least 300 patients over 2 years.

Eligible participants who receive care at DFCI and are identified using 02-180, 17-000, or other thoracic oncology protocols will be referred to the study website to complete the enrollment process using the electronic consent form rather than using a paper version in clinic.

5.5 PLASMA RESPONSE

Plasma response can also be assessed quantitatively through serial measurement of plasma genotyping. This phenomenon has been better studied in patients with advanced EGFR-mutant NSCLC. For example, a translational analysis assessing EGFR mutant copies in plasma ctDNA was done within the FASTACT-2 study. This was a randomized, double-blind, Phase III study of intercalated erlotinib or placebo with chemotherapy followed by maintenance erlotinib or placebo in previously untreated advanced NSCLC patients²¹

[figure not shown]

Figure 1. Dynamic change in EGFR mutant cfDNA at baseline, cycle 3, and progression (PD). GC+E, erlotinib plus chemotherapy; GC+P, placebo plus chemotherapy. ^aCopy/mL 0.1 were undetectable²¹.

In the subset of patients with EGFR mutations there was a strong correlation between the dynamics of EGFR mutations detected in cfDNA and the radiologic assessment performed at cycle 3 and at progression (**Figure 1**). The same approach is now feasible for ALK mutations with current available plasma NGS assays and could be now done in ALK positive NSCLC patients²². Furthermore, studies of plasma genotyping performed by Sacher and colleagues and as part of the AURA trial support that decreases in EGFR mutant clones in plasma ctDNA correlate with higher tumor responses while persistence or increase correlate with treatment failure (**Figure 2**).^{23, 24}

[figure not shown]

Figure 2. PFS based on clearance or detection of EGFR mutations in plasma samples taken A) 3 weeks and B) 6 weeks post initiation of osimertinib.²³

Those changes can be found in plasma early after treatment initiation and before the first tumor assessment usually done after 6-8 weeks on treatment. In ALK-mutated lung cancers, we expect to observe a similar phenomenon in which levels of ALK mutant clones will decrease in lung cancers exhibiting higher tumor responses.

Title: Study of Plasma Next Generation Sequencing for Remote Assessment,
Characterization, Evaluation of Patients With ALK Drug Resistance (**SPACEWALK**)

6 COLLABORATORS

6.1 ADDARIO LUNG CANCER MEDICAL INSTITUTE

The Addario Lung Cancer Medical Institute (ALCMI, voiced as "Alchemy") was founded by advanced stage lung cancer survivor [name] in 2008 as a 501(c) (3) non-profit organization. Working in tandem with its "partner" foundation the [name] Lung Cancer Foundation (ALCF), ALCMI and ALCF contribute resources and join together to power collaborative, patient-centric initiatives like this trial.

ALCMI does not serve the role of a traditional advocacy organization (education, awareness, grant making- -these are functions that ALCF takes on, plus much more) but instead is focused on patient-centric research advancements, directly facilitating and driving initiatives in genetic (molecular) testing, therapeutic discoveries, targeted treatments and early detection.

ALCMI has offices in California and biorepositories in California and Massachusetts, along with mature data banks and study management systems. ALCMI has built a one-of-a-kind lung cancer research consortium currently comprised of 24+ member institutions in the US, UK, and Europe, all working together as a team to catalyze and accelerate discovery, development and delivery of new, more effective lung cancer treatment options.

To bring form to this consortium, ALCMI developed and executed a Master Collaboration Agreement (identical) among all Member Institutions, governing centralized study development, contracting and budgeting, control of biospecimens and data, publication of results, intellectual property, indemnification and much more. Member Institutions are motivated to join the ALCMI consortium as it's a trusted, patient-founded/-focused Site Management Organization ensuring both scientific and patient advancements. Investigators at ALCMI member institutions often contribute their time and effort to advance our investigator-initiated, collaborative research, and similarly indirect costs are capped in order to ensure that our philanthropic-sourced funding are maximally employed. ALCMI develops the centralized systems and study management, while each of the participating Member Institutions may contribute their clinical and scientific resources for specific initiatives.

By providing access to critical masses of patient stakeholders, academic, community and industry researchers, ALCMI is making progress towards its goal of transforming lung cancer into a chronically managed disease by 2023.

6.1.1 ALCMI Biorepository

Thousands of new cases of lung cancer are diagnosed annually in ALCMI's academic and community institutions. The resultant ALCMI Biorepository is comprised of high-quality, standardized, annotated biospecimens, and serve as an open resource to academic and community researchers in the US. It will also form a foundation for collaboration with the National Institutes of Health and the biopharmaceutical industry for target/agent discovery and validation, genomics and proteomics—thus bringing new and improved treatment options to lung cancer patients in need.

The ALCMI Biorepository is structured as a single resource comprised of biospecimens from all ALCMI research projects.

As outlined in detail in the ALCMI Master Collaboration Agreement executed by all collaborating institutions, the rights to control and use of these banked biospecimens remain solely with ALCMI, specifically under the scientific review and prioritization oversight of the Scientific Leadership Board (SLB) of ALCMI. The SLB is comprised of representative scientists and clinicians from among the participating ALCMI Collaborating Institutions, plus a lay member appointed by ALCMI to bring the patient perspective to the deliberations.

6.1.1.0 *Biospecimen Distribution*

The ALCMI Biorepository is designed to be an ongoing effort, and will facilitate certain to-be-defined research studies. Specimens will be available to ALCMI investigators and outside collaborators upon formal application and approval. All proposals are reviewed and prioritized by the ALCMI SLB, employing a research request application and procedure by which requests are prioritized based on scientific merit, resource utilization, etc.

6.1.2 ALCMI Data Repository

The ALCMI Data Repository enables centralized biological specimen tracking from initial collections through the course of treatment/outcomes to comply with regulations (such as GCPs and GLPs), satisfy study subject consent requirements, enhance scientific accuracy, and improve development efficiency.

Title: Study of Plasma Next Generation Sequencing for Remote Assessment, Characterization, Evaluation of Patients With ALK Drug Resistance (SPACEWALK**)**

The sites' research coordinators/tissue procurement staff/data managers enter biospecimen information, subject demographics, clinical and laboratory data into the ALCMI Data Repository. ALCMI investigators and approved staff will have web-based access to this system, subject to user-level security privileges and compliance with applicable privacy regulations, including HIPAA as indicated below. A primary objective of ALCMI is to maintain subject confidentiality and assurance of informed consent for each biospecimen and data element procured.

The ALCMI Data Repository streamlines and optimizes lung cancer investigators' collaborative research efforts by providing intricate chain of custody for biospecimen transfers, detailed location and shipment management of biospecimens, aliquot, derivative, and pooled specimen tracking, and electronic signature capture upon transfer and disposition of biospecimens. These functions ensure that the tissue and data repositories remain in compliance with regulatory requirements and thus help to ensure that biospecimens used in ALCMI research and discovery efforts are of the very highest quality.

The ALCMI Data Repository and Biorepository enables researchers to collect, manage and access comprehensive (de-identified to all except the contributing investigator and their authorized institutional colleagues) clinical data, medical histories, and critical proteomic, genomic and phenotypic data associated with biospecimens in compliance with HIPAA and other regulatory requirements. Access to the ALCMI Data Repository is regulated by role-based security, with no capability by ALCMI staff and/or investigators and/or their staff to directly access the underlying database, unless specific permission is required for study activities.

ALCMI's data repository was developed and is managed by ClinCapture, a private cloud-based and electronic Data Collection (eDC) and Data Management Repository system.

6.2 RESOLUTION BIOSCIENCES

The haploid human genome contains 3 billion bases. Some driving mutations are single nucleotide variations (SNVs), where a single base change has occurred. For example, an adenine (A) becomes a guanine (G). Some of the SNVs are heterozygous mutations, so instead of 1 in 3 billion, it's actually a mutation of 1 in 6 billion bases. If trying to reach a detection limit of 0.1% of ctDNA in 99.9% background cfDNA, the problem becomes the ability to detect one molecule in 6 trillion bases.

Complicating the analysis, the cfDNA is broken into millions of short fragments. The average length of cfDNA is only 165 bases. Purified cfDNA from plasma appears predominantly as monomeric, dimeric, and occasionally trimeric nucleosome-sized DNA fragments. These short fragments must be mapped against the human genome to find out what gene they belong to and if they contain mutations of clinical significance.

Resolution starts with a standard blood draw — a liquid biopsy. The whole blood is spun down in a centrifuge to separate plasma from the buffy coat and red-blood cell fractions to eliminate leukocytes (white blood cells) as they contain DNA that if allowed to lyse, contribute greatly to the background noise. Variable amounts of high molecular weight genomic DNA found in the plasma, presumably derived from nucleated blood cells that lyse, are also observed and excluded.

**Title: Study of Plasma Next Generation Sequencing for Remote Assessment,
Characterization, Evaluation of Patients With ALK Drug Resistance (**SPACEWALK**)**

The cfDNA is extracted from the plasma for analysis. Through a series of proprietary biochemical steps, we amplify the cfDNA and using very small probes, target and capture strands of ctDNA. Resolution's novel chemistry allows for a very even and deep capture of DNA sequences, regardless of GC content. This ability has two benefits: Resolution can easily capture any area of the genome equally and they do not have to sequence deeply to gather enough information to make a variant call. Their on-target rate is incredibly high, yielding > 95% sensitivity and 100% specificity. The lower level of detection is a mere 0.1%.

Unlike PCR-based methods, Resolution's system can discover mutations. They do not need to "pre-program" specific variant sequences prior to capture. The Resolution platform can find SNPs, insertion and deletions, copy number variations (CNVs) / amplifications, and fusions / translocations. Critically, we can find fusions without any prior knowledge of the fusion partner or specific breakpoint.

The extreme efficiency of the Resolution Bio ctDx™ platform allows us to analyze multiple patient samples on a single desktop sequencer run. The resultant data is just a few GBs — up to 250x less than some other methods. The result is faster turnaround time and lower cost. Resolution currently run assays within their CLIA lab.

6.3 STUDY ROLES OF SUPPORTING LABORATORIES & SERVICE PROVIDERS

- a) Dana Farber Cancer Institute – Investigative site for this study
- b) ALCMI – Provide study management, ALCMI Biorepository (specimen collection kits creation and distribution) and ALCMI Data Repository
- c) Resolution Bioscience – Perform cfDNA testing on liquid biopsy specimens
- d) Laboratory for Computational Imaging Analysis at Columbia University – Analyze imaging results.

7 OBJECTIVES

7.1 PRIMARY OBJECTIVES

To study the relationship between specific ALK resistance mutations and specific next generation ALK TKI received before progression and/or the number of ALK TKIs received.

7.2 SECONDARY OBJECTIVES

- To study the feasibility, sensitivity, and turnaround time of plasma NGS in lung cancer patients with ALK TKI resistance.
- To study the outcomes of patients with ALK TKI resistance depending upon resistance mechanism detected and subsequent therapy received.
- To study the relationship between plasma NGS results from plasma specimens to advanced ALK positive NSCLC subjects on progression to a next generation ALK TKI and treatment decisions.
- To explore the ability of plasma genotyping to identify novel ALK resistance mechanisms.

Title: Study of Plasma Next Generation Sequencing for Remote Assessment,
Characterization, Evaluation of Patients With ALK Drug Resistance (SPACEWALK)

8 STUDY DESIGN

8.1 REMOTE CONSENT & PLASMA NGS

Our overarching hypothesis is that we can conduct a remote consent study using plasma NGS to characterize ALK resistance mechanisms arising in ALK positive NSCLC patients with progression while on a next generation ALK TKI, and that the chances of response to further treatment with a different ALK TKI can be predicted using those plasma NGS results.

This study will attempt to prospectively assess the resistance mechanisms detected by a plasma NGS assay in patients with advanced ALK positive NSCLC and systemic progression outside the brain using a web-based remote consent form process. Subjects will be sent blood collection kits with the necessary materials for local draws and those specimens will be sent directly by the subjects to the central laboratory (Resolution Bioscience) for plasma NGS. Plasma NGS results will be returned to the subject, their treating physician and study team, aiming to be returned within 2 weeks by Resolution Bioscience. This will allow prospective characterization of ALK resistant mutations arising in subjects after progression on different specific ALK TKIs. In addition, subsequent treatments and radiologic assessments received by the subjects will be prospectively monitored. A correlation between the ALK resistance mechanisms present at baseline, treatments received before and after plasma NGS assessments and outcomes will be analyzed.

We further propose here that plasma NGS could grant the ability to non-invasively detect specific ALK resistance mutations and, therefore, predict the sensitivity to different ALK TKIs and patients' outcomes. However, prospective CT-based response assessment is not feasible with a remote participation approach. We will instead use time to treatment discontinuation (TTD) as an alternate outcome. In collaboration with the US Food and Drug Administration (FDA), we found that TTD closely correlates with PFS outcomes in patients with genomic-driven lung cancer treated targeted therapies (manuscript in development), and is thus, well suited for studies of real-world evidence like ours. As such, we propose to evaluate the next treatment received by the subjects using TTD as the a time endpoint to assess treatment benefit. We also plan to analyze if plasma NGS results have any impact on the treatment decision process and if alterations in other relevant genes can impact subjects' outcomes.

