10.6 RADIOLOGY IMAGE COLLECTION & ANALYSIS

To characterize tumor response and study patient outcomes, CT images from subjects will be collected by the study staff and transferred to the Laboratory for Computational Imaging Analysis at Columbia University. This will be an exploratory analysis as we cannot control the quality and timing of these scans. This imaging analysis will complement the plasma response analysis.

Study staff will assist in obtaining copies of CT scans. For study staff to request copies of CT scan, study participants will be asked to complete a release form allowing their records to be obtained. The study staff will obtain the CT scans for all subjects and the release forms will be maintained in a locked filing cabinet. Up to 25 CT scans will be collected per subject, depending upon availability. PHI embedded in the images will be de-identified by the Laboratory for Computational Imaging Analysis at Columbia University prior to analysis. Using computer-aided-diagnosis software, each scan will be assessed. When serial imaging is available, change in nodule size will be characterized. Because each scan will already have undergone clinical review, no findings from the CT image analysis will be reported back to the subject.

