12 STATISTICAL CONSIDERATIONS

12.1 STUDY DESIGN & ENDPOINTS

A total of 300 subjects will be enrolled. Of those, we assume approximately 53% of the subjects (n=160) will have DNA shed and detectable ALK rearrangements, and will have progressed on either alectinib or ceritinib. Of the 160 subjects, we assume 80 subjects will have progressed on alectinib and 80 subjects will have progressed on ceritinib. Table 1 below shows the expected distribution of resistance mutations among these subjects.

Table 1: Expected distribution of resistance mutations

ALK mutation	Frequency after ceritinib	Frequency after alectinib
C1156Y	5%	0%
F1174X	15%	0%
I1171X	0%	10%
L1196M	0%	5%
G1202R	20%	30%
G1202del	5%	5%
D1203N	2%	0%
L1198F	5%	0%
C1156Y + L1198F	2%	2%
F1245C	0%	2%
No mutation	46%	46%

We will focus on two key mutational differences, F1174X and I1171X. With a type I error of 0.10, we have 99.8% power to detect the shown difference in acquiring the F1174X mutation, and 95.3% power to detect the shown difference in acquiring the I1171X mutation.

We will investigate response and time to treatment discontinuation (TTD) of those patients who have acquired an ALK mutation on their respective potential targeted therapy.

Table 2 below summarizes the maximum width of a 90% exact binomial confidence interval for response (CR+PR) to potential targeted therapy, per ALK mutation status.

Title: Study of Plasma Next Generation Sequencing for Remote Assessment, Characterization, Evaluation of Patients With ALK Drug Resistance (SPACEWALK)

Table 2: Max Width of 90% Exact Binomial Confidence Interval

ALK mutation	Total Sample Size	Number of Responses	Max Width of 90% CI
C1156Y	4	2	0.8043
F1174X	12	6	0.5093
I1171X	8	4	0.6143
L1196M	4	2	0.8043
G1202R	40	20	0.2779
G1202del	8	4	0.6143
D1203N	2	1	0.9491
L1198F	4	2	0.8043
C1156Y + L1198F	4	2	0.8043
F1245C	2	1	0.9491

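### CR+PR per mutation in section 12.1 and Table 2 has no defined criteria or reliable source, and the Table 2 widths are a best case that assumes every carrier is evaluable

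*Combined protocol and SAP*

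**What the plan says.** Section 12.1 commits to two outcomes after the plasma result: "We will investigate response and time to treatment discontinuation (TTD) of those patients who have acquired an ALK mutation". Table 2 then states the "maximum width of a 90% exact binomial confidence interval for response (CR+PR) to potential targeted therapy", by mutation, for ten mutation groups of 2 to 40 subjects. Nothing in 12.1 labels the response analysis exploratory.

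Section 8.1 takes a different position: "However, prospective CT-based response assessment is not feasible with a remote participation approach". It continues: "We will instead use time to treatment discontinuation (TTD) as an alternate outcome". Earlier in the same section it says that the radiologic assessments subjects receive will be monitored.

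Section 10.6 is the only imaging analysis. Its stated purpose includes characterising tumour response, and study staff are to obtain CT scans for all subjects, up to 25 each. It is called exploratory because scan quality and timing are outside the study's control. Its output is limited: "When serial imaging is available, change in nodule size will be characterized".

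Footnote 6 of the section 10.11 calendar restricts follow-up requests for records and imaging to subjects who could not be reached. For the others, progression and treatment changes are reported by the subject.

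**The concern.** The plan sets a precision for an outcome that another section replaces, and that no procedure turns into data. The clinical data list in 10.5 has no response item. The follow-up in 10.8 asks about therapy outcome until treatment stops or a new systemic therapy begins, with no response category. There are no response criteria, named baseline scan, scan schedule, rule for assigning CR or PR, or definition of who is evaluable.

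The second objective in section 7.2 concerns outcomes by resistance mechanism and subsequent therapy, and Table 2 is the plan's statement of how precisely response would be known for each mutation. Without a rule fixed in advance, any reported CR+PR rate would depend on choices left open in the plan. It would also come from the subjects who happen to have usable serial scans, who may differ from the other carriers.

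**Working it through.** **1. Table 2 reproduced.** The inputs from 12.1 are the 90% level, the exact method, and responses equal to half of each n. The two-sided Clopper-Pearson limits with α = 0.10 are: lower = Beta quantile(0.05; x, n−x+1), upper = Beta quantile(0.95; x+1, n−x).

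| n | x | Limits | Width | Table 2 |
|---|---|---|---|---|
| 2 | 1 | 0.0253 to 0.9747 | 0.9494 | 0.9491 |
| 4 | 2 | 0.0976 to 0.9024 | 0.8048 | 0.8043 |
| 8 | 4 | 0.1929 to 0.8071 | 0.6142 | 0.6143 |
| 12 | 6 | 0.2453 to 0.7547 | 0.5094 | 0.5093 |
| 40 | 20 | 0.3611 to 0.6389 | 0.2778 | 0.2779 |

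All agree to within 0.0005, so the arithmetic is not at issue.

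**2. Who is counted.** Section 12.1 states: "we assume 80 subjects will have progressed on alectinib and 80 subjects will have progressed on ceritinib". Expected carriers are therefore 80 × (ceritinib % + alectinib %) from Table 1:

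- G1202R: 80 × (0.20 + 0.30) = 40
- F1174X: 80 × 0.15 = 12
- I1171X: 80 × 0.10 = 8
- G1202del: 80 × (0.05 + 0.05) = 8
- C1156Y, L1196M and L1198F: 80 × 0.05 = 4 each
- C1156Y + L1198F: 80 × (0.02 + 0.02) = 3.2, shown as 4
- D1203N and F1245C: 80 × 0.02 = 1.6 each, shown as 2

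Every row of Table 2 equals the full expected number of carriers, rounded up where needed. No allowance is made for carriers who never start the targeted therapy or who lack usable scans.

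**3. Where CR or PR could come from.**

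| Section | What it supplies | CR/PR category? |
|---|---|---|
| 8.1 | Prospective CT response not feasible; TTD instead; radiologic assessments monitored | No |
| 10.5 | Demographics, cancer characteristics, cancer and treatment history | No |
| 10.6 | Exploratory size change where serial scans exist; scans for all subjects | No |
| 10.8 | Therapy outcome until treatment failure | No |
| 10.11, footnote 6 | Follow-up imaging only if the subject is not reached | No |
| 12.1 | CR+PR analysed per mutation | Assumed |

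Sections 10.6 and 10.11 also disagree on whether on-treatment scans will be obtained routinely.

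**4. What incomplete evaluability would do.** The documents give no evaluable share, so the shares below are assumptions. The method is as in step 1, with x = n/2.

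| Share assumed | G1202R n | Width |
|---|---|---|
| 100% | 40 | 0.278 |
| 75% | 30 | 0.322 |
| 50% | 20 | 0.396 |
| 25% | 10 | 0.555 |

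For F1174X, the width goes from 0.509 (n = 12) to 0.694 at a 50% share (n = 6).

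**5. Would a fixed-time TTD proportion serve as a substitute?** Under the exponential assumption of 12.1, the proportion still on therapy at 6 months is 0.5^(6/median). This gives 0.5^(6/5) = 43.5% at a 5-month median and 0.5^(6/10) = 66.0% at 10 months. The chance that the lower limit of an exact 90% interval exceeds 43.5% when the truth is 66.0%, with all subjects followed to 6 months, is:

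- n = 40: 83%
- n = 12: 37%
- n = 8: 18%
- n = 4: 19%

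Only the G1202R group separates the two scenarios reliably.

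**The case against.** The other side has four arguments.

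- **Section 8.1 is narrower than it may look.** A reader might infer that response cannot be assessed at all in this design. The documents do not support that. Only prospective CT assessment is called infeasible, and the same section says that radiologic assessments will be monitored. A retrospective read of clinical scans is not excluded.
- **Section 10.6 does collect scans in order to characterise tumour response.** A reader might infer that the trial yields nothing from which response could be built. That too is stronger than the text allows, because serial size change is raw material for a response category. What is missing is the rule, the evaluable set and an agreed supply of scans.
- **The consequences are bounded.** The primary objective in 7.1 concerns mutation by prior TKI. Response is not named in the secondary objectives. Table 2 carries no test or decision, and TTD is already planned with Kaplan-Meier, Cox and log-rank methods.
- **A 6-month on-treatment proportion is not an obvious replacement.** It dichotomises an outcome that 12.1 already analyses in full. Restricting it to complete follow-up keeps early stoppers and drops subjects censored on therapy, which biases the proportion downward.

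All four stand as limits on the point. None supplies a definition of CR or PR, and none reconciles 12.1 with 8.1 or 10.6 with 10.11.

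**Conclusion.** The point holds in a bounded form. Section 12.1 presents CR+PR per mutation as a planned analysis with stated precision, while 8.1 replaces it with TTD and no section collects or derives it. At best there is an exploratory size read in subjects with serial scans, and the documents disagree on whether follow-up scans are routinely requested.

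This is more than missing detail, because the Table 2 precision cannot be delivered as written. All ten rows are affected, and the stated widths are a best case. How far short the precision would fall depends on the evaluable share, which the documents do not give; the widths at 75%, 50% and 25% illustrate this and are not forecasts.

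The arithmetic of Table 2, the primary objective and the planned TTD analysis are not in question.

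**What to change.** 1. Reconcile sections 8.1, 10.6, 10.11 (footnote 6) and 12.1, so that they agree on the role of tumour response and on which subjects' scans are obtained during follow-up.
2. In 12.1, make TTD the per-mutation outcome, reported as Kaplan-Meier estimates with 90% intervals.
3. Move tumour response to an exploratory analysis of size change among subjects with a baseline scan and at least one on-treatment scan. Report the number evaluable beside the number of carriers in each mutation group.
4. Remove Table 2, or relabel it as a best case under full evaluability.
5. Optionally, report the Kaplan-Meier proportion still on therapy at a fixed time as a summary of TTD. Use all carriers who start therapy, not only those with complete follow-up, and do not claim that it separates the scenarios in the small mutation groups.

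The cost is a revision of wording in the protocol and analysis plan, with no new data collection needed for TTD. The downside is that no formal response rate is reported, which 8.1 already concedes.
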